
Group 1. Basal bolus with glargine U300 once daily and glulisine insulin before meals (n=90).

Group 2. Basal bolus with glargine U100 once daily and glulisine insulin before meals (n=90).

IV.d. Basal Bolus Insulin Protocol.

Patients will be treated with a basal bolus insulin regimen as previously reported (15, 16, 39). In brief, subjects treated with insulin prior to admission will receive 80% of the total daily outpatient insulin dose given. Insulin naïve patients will discontinue oral agents and will receive a starting total daily dose (TDD) of 0.4 U/kg/day for BG between 140 mg/dl and 200 mg/dL and 0.5 U/kg/day for BG between 201 mg/dl and 400 mg/dL. The starting TDD will be reduced to 0.3 U/kg/day in patients \geq 70 years or with a GFR < 60 ml/min. Both groups will be treated with bolus regimen given half of TDD as basal (glargine U300 or U100) once daily and half as insulin glulisine divided in three equal doses before meals. Patients with poor oral intake or to be kept NPO will receive the basal dose, but prandial dose will be held (32). Insulin dose will be adjusted daily to maintain a fasting and pre-dinner BG between 80 mg/dl and 180 mg/dl.

IV. e Treatment randomization. This is an open label randomized controlled trial. Patients will be randomized 1:1 consecutively using a computer generated randomization table provided by [name], statistician at the Emory School of Public Health. The randomization table will be mailed to the research pharmacist at each institution who will be in charge of the randomization and group assignment. A research pharmacist at each institution will follow a computer-generated block randomization table based on prior insulin use (yes/no).

IV.f TREATMENT PROTOCOL - Basal Bolus Insulin Regimen with Glargine Once Daily plus Glulisine before Meals

Patients Treated with Insulin Prior to Admission

- Discontinue oral antidiabetic drugs on admission.

Subjects treated with insulin prior to admission will receive 80% or 100% of the total daily dose (TDD) given as basal bolus regimen. **Starting Insulin Doses:**

- Randomization BG <200mg/dl-give 80% of the TDD*
- Randomization BG>200mg/dl-give 100% of the TDD*
- Half of TDD will be given as basal (glargine U300 or U100) and half as rapid-acting insulin.
- Glargine U300 and U100 will be given once daily, at the same time of the day.
- Patients will receive the full-dose of glargine (even if NPO) the day of surgery or diagnostic procedure(s).

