- Glulisine insulin will be given in three equally divided doses before each meal. To prevent hypoglycemia, if a subject is not able to eat, glulisine insulin dose will be held.

* If patient was on basal only therapy consider adding prandial dose as calculated above.

Insulin Naïve Patients Treated with Oral Agents or GLP1-RAs Prior to Admission

- Discontinue oral antidiabetic drugs on admission.
- Starting total daily insulin dose:
 - 0.4 U/Kg/day when randomization BG between 140-200 mg/dL
 - 0.5 U/Kg/day when randomization BG between 201-400 mg/dL
 - Reduce TDD to 0.3 units per kg in patients ≥ 70 years of age and/or with an eGFR < 60 ml/min.
- Half of TDD will be given as glargine U300 or U100 and half as glulisine.
- Glargine will be given once daily, at the same time of the day.
- Patients will receive the full-dose of glargine insulin (even if NPO) the day of surgery or diagnostic procedure(s).
- Glulisine insulin will be given in three equally divided doses before meals. To prevent hypoglycemia, if a subject is not able to eat, the dose of glulisine will be held.

Supplemental insulin. Glulisine insulin will be administered following the “supplemental/correction insulin scale” protocol (Appendix 1).

- If a patient is able and expected to eat most of his/her meals, supplemental insulin will be administered before meals and at bedtime following the “usual” dose of the insulin scale protocol.
- If a patient is not able to eat, supplemental insulin will be administered every 6 hours following the “sensitive” dose of the supplemental insulin scale protocol.

Basal Insulin adjustment.

- Daily basal (glargine U300 and U100) insulin dose will be adjusted as follow:

- If the fasting and pre-dinner BG is between 100 - 140 mg/dl in the absence of hypoglycemia the previous day: no change
- If the fasting and pre-dinner BG is between 141 - 180 mg/dl in the absence of hypoglycemia: increase basal insulin by 10% every day
- If the fasting and pre-dinner BG is 181- 299 mg/dl in the absence of hypoglycemia the previous day: increase basal insulin (glargine) dose by 20% every day
- If the fasting and/or pre-dinner BG is ≥ 300 mg/dl in the absence of hypoglycemia the previous day: increase basal insulin (glargine) dose by 30% every day
- If the fasting and pre-dinner BG is between 70 - 99 mg/dl in the absence of hypoglycemia: decrease TDD (basal and prandial) insulin dose by 10% every day

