events, number of severe hyperglycemia, mean daily fasting BG, daily insulin dose, length of hospital stay, acute renal failure and hospital mortality. Blood glucose will be measured before each meal and at bedtime. For discrete outcomes (such as hypoglycemia outcomes), if the outcome is binary (e.g. with or without hypoglycemia), we will first conduct nonparametric comparisons based on a two-sided Chi-square test (or Fisher's exact test in the presence of low incidence rates), followed by the Cochran-Mantel-Haenszel test, which adjusts for the potential center effect. If the discrete outcome is a count outcome (such as the number of hypoglycemic event), we will perform Poisson regression (or Negative Binomial regression) that adjusts for the length of hospital stay to assess the difference in the count outcome between the treatment groups. We also value the repeated measures analyses based on mixed effect models. This is because they will allow us to assess treatment effect fine tuned according to other confounders of the BG outcomes. By these considerations, we will conduct both types of analyses to provide a thorough evaluation of the hypothesis of interest. For continuous outcomes that are not repeated measures (such as length of hospital stay), we will use two-sample t-tests or nonparametric Wilcoxon tests to compare them between groups. Transformations will be applied if normality violation is detected. Multivariate linear regression will be further conducted to assess the difference in continuous secondary outcomes between the two groups while other relevant covariates. We will use standard model selection and model checking procedures for linear regression to decide the final models and assess their fits to the data.

IV.f. Data and Safety Monitoring Board (DSMB):

The Data and Safety Monitoring Board (DSMB) will review unblended data on safety, treatment compliance, and evaluate the efficacy of the intervention being studied in this clinical trial. The DSMB will meet at 6-month intervals and report on study progress to the IRB.

IV.g. Interim Analysis and Stopping Rules: We plan to perform one interim analysis on the primary endpoint every 6 months and when half of the subjects have been randomized. The trial will be stopped if there is evidence beyond a reasonable doubt of a difference in the rate of death and hospital complications (two-sided alpha level, <0.01) between the treatment groups.

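### Daily insulin dose has no unit, averaging window or component split, and its planned analysis does not fix the protocol-calculated starting dose as a covariate

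*Combined protocol and SAP*

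**What the plan says.** Section IV.g (Data Analysis, Analysis of Secondary Endpoints) includes among the Aim 1 secondary endpoints "mean daily fasting BG, daily insulin dose, length of hospital stay, acute renal failure and hospital mortality". Daily insulin dose is not in the secondary outcome list in IV.c. A unit appears only for the Aim 2 follow-up (V.e, units per day).

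For continuous outcomes that are not repeated measures, IV.g says "we will use two-sample t-tests or nonparametric Wilcoxon tests to compare them between groups". It also favours mixed models for repeated measures. It then adds a multivariable linear regression for continuous secondary outcomes, with covariates not named and the final model decided by model selection.

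IV.f (Treatment Protocol) sets the starting total daily dose (TDD) by rule:
- Insulin-naive patients: "0.4 U/Kg/day when randomization BG between 140-200 mg/dL" and "0.5 U/Kg/day when randomization BG between 201-400 mg/dL".
- Reduction for age or renal function: "Reduce TDD to 0.3 units per kg in patients ≥ 70 years of age and/or with an eGFR < 60 ml/min".
- Prior insulin users: "Subjects treated with insulin prior to admission will receive 80% or 100% of the total daily dose (TDD) given as basal bolus regimen". The choice depends on randomization glucose, for example "Randomization BG>200mg/dl-give 100% of the TDD".

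Half of TDD is basal glargine and half is scheduled glulisine. Correction glulisine comes on top: for patients who are eating, "supplemental insulin will be administered before meals and at bedtime following the" usual column of the Appendix 1 scale. IV.e blocks randomization on prior insulin use.

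**The concern.** Two things are at stake.

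**Precision.** Every input to the starting dose is known before allocation, and later basal changes are mostly percentage steps from it. An analysis that ignores the starting dose treats predictable spread as noise. Leaving it to model selection means nobody can say beforehand whether it will be in the model, or in what form.

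**Interpretation.** The randomized drug is the basal insulin, but patients receive three streams: basal glargine, scheduled glulisine and correction glulisine. Correction doses rise with glucose (3, 4, 5 and 6 units across 141 to 300 mg/dl in the usual column before meals). If the arms end with similar mean glucose, a reader will ask whether one arm needed more correction insulin to get there. The background section itself notes that U300's long action may limit day-to-day adjustment and that steady state comes on the second or third day, while the primary endpoint leaves out only the first day. An undefined dose endpoint with no component split need not answer that question.

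**Working it through.** **1. Evaluable number per arm.** The plan gives no SD, effect or power for dose, so the only stated figure to reproduce is the primary sample size (IV.g): margin 18 mg/dl, SD 45 mg/dl, true difference 0, one-sided test, 80% power. Alpha is not stated; one-sided 0.05 gives

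n = 2 × [(1.645 + 0.842) × 45/18]² = 77.3, rounded up to 78 per group.

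This matches the plan. Allowing for 10% attrition, 78/0.9 = 86.7, so 87; the plan uses 90. Of 90, 81 remain evaluable, and 81 per arm is used below.

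**2. Spread created by the dosing rules alone.** For insulin-naive patients at assumed weights of 70 and 130 kg:
- 70 kg × 0.3 U/kg = 21 U/day
- 130 kg × 0.5 U/kg = 65 U/day

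That threefold range exists before any treatment effect. It is the same in expectation in both arms, so it adds noise and not bias.

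**3. Gain from fixing the starting dose.** With R² the share of dose variance explained by the starting dose:
- Unadjusted SE = SD × √(2/81) = 0.157 SD; 95% half-width = 1.96 × 0.157 = 0.308 SD.
- Adjusted SE = unadjusted SE × √(1 − R²).

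| Assumed R² | Interval width ratio | Narrowing | Equivalent unadjusted n per arm, 81/(1 − R²) |
|---|---|---|---|
| 0.3 | 0.837 | 16% | 116 |
| 0.5 | 0.707 | 29% | 162 |
| 0.7 | 0.548 | 45% | 270 |
| 0.8 | 0.447 | 55% | 405 |

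**4. Is that range of R² plausible?** The documents do not give it, so the IV.f rules were simulated under assumptions: mean weight 95 kg with SD 20 to 25; 40 to 60% prior insulin users; median home dose 0.5 U/kg with log-SD 0.4 to 0.6; 35% on the reduced starting dose; randomization glucose mean 220 mg/dl, SD 60; in-hospital titration log-SD 0.2 to 0.4; correction insulin median 6 U/day with log-SD 0.8. Across these settings:
- R² for starting dose was 0.43 to 0.84.
- The half-width for total dose fell from about 7 to 14 U/day unadjusted to about 4 to 8 U/day adjusted.
- Weight and prior insulin use together explained only about 15% of the variance on average, so a generic adjustment set would miss most of the gain.

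**5. Can the starting dose be derived uniquely?** Not yet, for prior insulin users:
- The Basal Bolus Insulin Protocol summary (second section IV.d): 80% of the outpatient dose.
- IV.f: 80% or 100%, depending on randomization glucose.
- X.a (Hypoglycemia): a 20% reduction on admission.
- IV.f footnote, basal-only users: adding a prandial dose is to be considered, which leaves the total open.

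**The case against.** The strongest reply is that the plan already provides for adjustment. IV.g commits to a regression for continuous secondary outcomes, allows transformations and favours mixed models. The t-test and Wilcoxon sentence takes length of stay as its example, and a daily dose is arguably a repeated measure. A predictor as strong as the starting dose would probably survive any selection procedure that was offered it. All of this stands. What remains is that nothing says the starting dose will be offered, or that prior insulin use, the blocking factor, will be in the model.

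Several stronger readings are tempting, and the documents do not support them:
- **Dose will be compared as one raw total.** The text says neither raw nor total; it leaves the matter open.
- **The comparison is biased.** The same rules apply in both randomized arms, and allocation is blocked on prior insulin use.
- **The comparison is underpowered for a relevant difference.** No dose difference is named as relevant, and the trial is not sized on dose.
- **The correction scale hides a glucose gap of calculable size.** The documents give no glucose fall per unit of insulin, and a single slope ignores the step at 141 mg/dl and the separate bedtime scale.
- **A component split would show that extra correction insulin produces the similar glucose.** Correction dose is itself a post-randomization outcome, and scheduled insulin is also titrated to glucose. The trial compares regimens that both include correction insulin. A split shows whether use differed, not what caused the glucose result.

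**Conclusion.** The point holds as a matter of definition and prespecification for one secondary endpoint. Daily insulin dose has no unit, window or components, and a strong predictor that the protocol itself calculates before allocation is not fixed in the model. The arm comparison is unbiased, but its interval could be about 16 to 55% narrower if the starting dose explains 30 to 80% of dose variance. That range is an assumption. The simulation supports it (0.43 to 0.84), but only under assumed weights, home doses and titration spread. Without a component split, the planned analysis does not show whether correction glulisine use differed by arm, which readers will want beside a finding of similar mean glucose. The sample size and the validity of the primary comparison are not affected.

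**What to change.** Amend the secondary endpoint section as follows:
1. Define the endpoint as mean units/day after day 1 of therapy, up to 10 days, the same window as the primary endpoint. Report basal glargine, scheduled glulisine and supplemental glulisine separately.
2. Compare arms in one prespecified linear model, on the log scale if the dose is skewed, with two fixed covariates: the starting dose calculated from pre-randomization data (not the dose actually given) and prior insulin use. This replaces model selection for this endpoint.
3. Report the supplemental-glulisine difference with its confidence interval beside the mean daily glucose result, labelled as description and not as evidence of what caused similar glucose.
4. Reconcile the starting-dose statements for prior insulin users in the Basal Bolus Insulin Protocol summary, IV.f (including basal-only users) and X.a, so that the covariate can be derived. If they are not reconciled, use the inputs themselves, including home dose, as the fixed covariates.

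The cost is a little more analysis work and the reconciliation of those passages. The baseline inputs and administered doses are already needed to run the dosing protocol, so no new data and no more patients are required.

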Withdrawal criteria	x	x	x	x	x	x	x	x	x	x
Dose adjustment		x	x	x	x	x	x	x	x	x
Efficacy										
Vital signs ¹	x									x
Phys Exam ¹	x									x
Body weight	x									x
BMI	x									x
HbA1c	x									
Fasting BG	x	x	x	x	x	x	x	x	x	x
Pre-meal BG	x	x	x	x	x	x	x	x	x	x
Safety										

Adv events	x	x	x	x	x	x	x	x	x	x
Hypoglycemia	x	x	x	x	x	x	x	x	x	x
Urine pregnancy test	x									x
Trial material										
Drug dispense ²	x									

¹At time of study enrollment and hospital discharge ²As needed

Flow Chart: Aim 2, Outpatient Study

Visit Type	Hospital Day 1	TC	Clinic visit	TC	TC	TC	Clinic visit
Visit #	1	2	3	4	5	6	7
Time-wks	0	2	4	6	8	10	12
Inf. consent	x						
Incl/excl criteria	x						
Randomization	x						
Withdrawal criteria		x	x	x	x	x	x
Drug Compliance		x	x	x	x	x	x
Dose adjustment		x	x	x	x	x	x
Efficacy							
Vital signs	x		x				x
Phys Exam	x		x				x
Body wgt	x		x				x
BMI	x		x				x
HbA1c	x		x				x
Fasting BG	x		x				x
Safety							
Adv events	x	x	x	x	x	x	x
Hypoglycemia	x	x	x	x	x	x	x
Urine pregnancy test	x		x				
CMP or BMP	x		x				x
Trial material							
Drug dispense	x		x				
Drug account	x		x				x

IX. Potential Risks to the Subject:

IX.a. Hypoglycemia. It is possible that following the proposed protocol, patients receiving insulin glargine U300 and U100 may develop hypoglycemia. The risk of hypoglycemia in non-ICU patients treated with subcutaneous insulin is between 5–30% (12, 17, 41, 42). The number of hypoglycemia will be analyzed statistically. For the purpose of this analysis, hypoglycemia is defined as a BG < 70 mg/dL. Severe hypoglycemia is defined as BG < 40 mg/dL.

X. Protection against risks:

We will follow safeguards to minimize the risk to our subjects: a) we will carefully monitor capillary BG at the bedside using a hand-held glucose meter, b) only experienced nurses/or phlebotomist will draw blood samples, and c) women of reproductive age who are sexually active will undergo a urine pregnancy tests prior to participation in the study. To prevent significant clinical events, no patients with history of significant liver, renal impairment or cardiac failure will be recruited in this study.

X.a. Hypoglycemia: We expect that approximately 10% in the inpatient setting and ~20% in the outpatient (post-discharge) arm will experience one or more episodes of hypoglycemia. To minimize the risk of hypoglycemia, the starting dose will be reduced in the basal bolus insulin regimen (TDD: 0.3 units

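### The hypoglycemia analyses do not commit to prior insulin use, a randomisation stratum; if it is prognostic this may cost a little power, without bias

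*Combined protocol and SAP*

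**What the plan says.** **Randomisation (IV.e).** The allocation tables are blocked on one patient factor and held locally: "A research pharmacist at each institution will follow a computer-generated block randomization table based on prior insulin use (yes/no". Section VII lists four sites or site groups.

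**Binary outcomes (IV.g Data Analysis, Aim 1, Analysis of Secondary Endpoints).** The presence or absence of hypoglycemia is compared in two steps. The opening step has no strata: "we will first conduct nonparametric comparisons based on a two-sided Chi-square test (or Fisher's exact test in the presence of low incidence rates". The next step brings in the site as the stratum, being "followed by the Cochran-Mantel-Haenszel test, which adjusts for the potential center effect".

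**Event counts (same section).** "we will perform Poisson regression (or Negative Binomial regression) that adjusts for the length of hospital stay".

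**Other modelling (same section).** Mixed models are also planned because "they will allow us to assess treatment effect fine tuned according to other confounders of the BG outcomes". The confounders are not listed, and no analysis in the document names prior insulin use.

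**Why the factor may be prognostic (IV.f).** For one stratum, "Subjects treated with insulin prior to admission will receive 80% or 100% of the total daily dose (TDD) given as basal bolus regimen". The other starts from a weight-based rule, for example "0.4 U/Kg/day when randomization BG between 140-200 mg/dL". IV.d and X.a describe the starting dose of insulin-treated patients differently from IV.f. Those sections must be reconciled, but this point does not depend on how.

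**Aim 2 (V.g.2).** The Aim 2 outcomes, including hypoglycemia, follow the strategy set for the Aim 1 secondary endpoints, so the same gap carries over.

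**The concern.** When the arms are balanced within a stratum that predicts the outcome, differences between strata contribute almost nothing to the difference between arms. A test that ignores the stratum still counts them as noise. Its variance is too large, it rejects a true null less often than the nominal 5%, and it gives up some power.

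Fewer hypoglycemic events with U300 is a stated hypothesis of both aims, so this is the outcome on which the trial hopes to show an advantage. The trial is also open label and the covariates of the adjusted models are left open. Naming the randomisation factor in advance removes one later choice.

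**Working it through.** **1. The plan's own figure.** No power is stated for hypoglycemia. The only sample size is for mean daily BG: margin 18 mg/dl, SD 45 mg/dl, true difference 0, one-sided, 80% power. Alpha is not stated; one-sided 0.05 gives 2 × (1.645 + 0.842)² × (45/18)² = 77.3, rounded up to 78, and the exact t-test gives 77.97. The stated 78 per group therefore reproduces. 78/0.90 = 86.7, and the plan enrols 90 per group, 180 in total.

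**2. Events and strata.** X.a states: "We expect that approximately 10% in the inpatient setting" will have at least one episode. 0.10 × 180 = 18 patients with an event. Four sites × two prior-insulin groups = 8 strata, on average 18/8 = 2.25 events each.

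**3. Share of outcome variance due to the stratum.** With a fraction w of prior insulin users, stratum rates p1 (users) and p0 (naive), and overall rate p:

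share = w(1 − w)(p1 − p0)² / [p(1 − p)]

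The ignored-stratum variance is too large by the factor 1/(1 − share). The documents give neither w nor the stratum rates, so both are assumed; w = 0.5.

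| p1 / p0 | p | share | variance overstated by |
|---|---|---|---|
| 12% / 8% | 10% | 0.0004/0.09 = 0.4% | 0.4% |
| 15% / 5% | 10% | 0.0025/0.09 = 2.8% | 3% |
| 18% / 2% | 10% | 0.0064/0.09 = 7.1% | 8% |
| 20% / 5% | 12.5% | 0.005625/0.109375 = 5.1% | 5% |
| 30% / 5% | 17.5% | 0.015625/0.144375 = 10.8% | 12% |
| 45% / 15% | 30% | 0.0225/0.21 = 10.7% | 12% |

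Only the first three average the 10% that X.a expects. The last sits at the top of the 5–30% range in IX.a. At 15%/5%, moving w to 0.3 or 0.7 gives shares of 2.9% and 2.0%.

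**4. Simulated CMH test, by centre against by centre × prior insulin use.** Assumptions: 180 patients, four centres with 40/30/15/15% of patients and modest centre effects, half on prior insulin, blocks of 4 within centre × prior insulin use, two-sided 5%, no continuity correction, U300 odds ratio 0.3 for power, 8000 trials per setting. Monte Carlo standard error is about 0.25 points for type I error and up to 0.6 for power.

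| U100 rates, users / naive | Type I error: centre → both | Power: centre → both |
|---|---|---|
| 10% / 10% | 5.3% → 5.4% | 44.7% → 44.9% |
| 12% / 8% | 4.9% → 5.0% | 45.0% → 44.9% |
| 15% / 5% | 4.5% → 4.7% | 44.5% → 45.1% |
| 18% / 2% | 3.7% → 4.5% | 42.2% → 44.5% |
| 45% / 15% | 4.2% → 5.1% | 83.6% → 85.5% |

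The unstratified test behaves almost like the centre-only CMH test (power 44.2% at 15%/5%, 42.2% at 18%/2%).

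Further runs at odds ratio 0.4:
- 15%/5%: power 27.0% → 28.4% with 160 patients and 30.2% → 31.2% with 176.
- 20%/5%, 164 patients: power 33% → 35%, type I error 4.4% → 4.8%.
- 30%/5%, 164 patients: power 40% → 43%, type I error 3.7% → 4.9%.

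**5. Scale.** Unstratified power with 90 per arm is 24.5% for 10% against 5%, and 47.8% for 10% against 3%. The low event count limits this comparison far more than the missing stratum does.

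**6. Rare outcomes.** At assumed rates of 2%/1% with 160 patients, 0.015 × 160 = 2.4 events are expected and about 6 of 8 strata have none. Both CMH versions then reject equally often (1.9%).

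No figure was computed for the count model or for Aim 2. The sizes above apply to the inpatient tests of proportions.

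**The case against.** The strongest reply is that the loss depends on something the documents never show. No section gives hypoglycemia rates by prior insulin use. Different starting-dose rules do not establish different risk, because IV.f adjusts doses daily. The background cites 3% hypoglycemia in medicine and 12% in surgery patients, but that contrast is by service. The medicine trial enrolled insulin-naive patients, so service and prior insulin use cannot be separated. This stands: the loss is conditional, and every stratum rate above is an assumption.

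A reader might infer that the plan excludes the stratum. It does not. The planned mixed models could include prior insulin use, and the text does not say that length of stay is the only term in the count model. What remains is that nothing commits to the factor.

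The design is also partly respected. The block tables are held at each institution, so centre may itself be a randomisation stratum, which the CMH test already uses. The remedy therefore keeps centre.

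Eight strata with about 18 events are sparse. In the simulations the eight-stratum test kept its error between 4.5% and 5.4%, and it lost essentially nothing where the strata did not differ or barely differed. Sparse strata still need a stated rule, since actual site sizes are unknown.

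Finally, precision should not be claimed too widely. Adjusting helps the test and the risk difference, but need not narrow the interval for an odds ratio.

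**Conclusion.** The point stands as a minor improvement. The randomisation factor is not committed to in any hypoglycemia analysis. If it predicts hypoglycemia, the planned tests of proportions are slightly conservative. Where the assumed rates average 10%, adding the stratum changes power by roughly 0 to 2.3 points, about 1 point at 15%/5%. The gain reaches about 3 points only at 30%/5%, which averages 17.5%. These sizes rest on assumed stratum rates, an even split by prior insulin use, assumed centre shares and odds ratios of 0.3 or 0.4.

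Three stronger readings are not supported:
- **That the comparison is invalid.** There is no bias, and the error rate falls slightly below nominal rather than above it.
- **That precision is certainly lost.** If prior insulin use does not predict hypoglycemia, nothing is lost.
- **That all binary safety outcomes are affected.** For severe hypoglycemia or death, events are too few for the stratum to matter.

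Nor would the change make hypoglycemia a well-powered comparison.

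**What to change.** In IV.g Data Analysis, Analysis of Secondary Endpoints:
- State that the CMH test for hypoglycemia (BG < 70 mg/dl) is stratified by institution × prior insulin use, using the stratum recorded at randomisation.
- Include institution and prior insulin use as terms in the Poisson or negative binomial model, alongside length of stay.
- State in advance that an exact stratified test is used, or small sites are combined, if strata are sparse.
- Keep the planned Fisher test for rare outcomes such as severe hypoglycemia and death.

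State in V.g.2 that the Aim 2 hypoglycemia analysis uses the same factors.

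The cost is a few sentences and no extra patients. The pharmacist must know the stratum to allocate treatment, so it should be available. The protocol does not say that it is entered in the study database, and this should be confirmed. The one small downside is the sparse strata, which the third item covers.
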